Institutional Review Board Intervention/Interaction Detailed Protocol

Principal Investigator:	[name], DPM, PhD
Project Title:	A test of efficacy and foot position alteration in patients wearing Good Feet arch supports for the treatment of pain
Version Date:	09/15/22
Version Name/Number:	GF-20222

For Intervention/Interaction studies, submit a Detailed Protocol that includes the following sections. If information in a particular section is not applicable, omit and include the other relevant information.

1. Background and Significance

Foot orthoses are arch supports that can be worn in the shoes, and are designed to relieve pain by providing support to various areas of the foot to eliminate or reduce excessive mechanical forces. Most commonly, these devices are used as part of the treatment protocol for a variety of common foot ailments including painful plantar fasciitis and pronation. A variety of musculoskeletal pains have been shown to be reduced, and stability in ambulation can be improved by adding arch support to the shoes (1-9). Most importantly, previous studies have demonstrated that the structure of the foot can be altered, and with that the function of the foot, when orthoses are used.

A study by Nawoczenski, et al (1) used an electromagnetic tracking device to record the relative position and orientation of the hallux relative to the calcaneous during walking, with and without an arch support. This system verified that the position of the first metatarsal in particular varied depending on the arch support worn. Utilizing a forefoot pressure transducer, Yung-Hui, et al (2) showed that the magnitude of forefoot pressure could be changed by varying the height of the heel from 1.0 to 7.6cm, and that the amount of forefoot pressure could be modulated with the addition of various types of shoe inserts and arch supports. With arch supports, they showed a decrease in impact force of 33.2%, and a reduction in heel pressure and forefoot pressure by about 24%. They found that arch supports increased the level of comfort that these subjects had during walking as compared to those without arch supports.

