Finally, this principal investigator previously published a related study in 2009 (8), which examined the effect of over-the-counter foot orthoses on several parameters including flexible foot deformities (i.e. hammertoes, and hallux valgus), as well as foot, knee, hip and back pain. Balance was also examined. In the previous study, radiographs were used to document variations in arch height, intermetatarsal angle, hallux abductus angle, metatarsal declination angle, calcaneal inclination angle, and sesamoid position, and several statistically significant differences were documented with and without arch supports. In addition, center of pressure measurements were also used to document shifts in center of mass with time, as a measure of stability while standing. There was also a statistically significant improvement in stability when arch supports were used. Symptomatic changes were also measured, and that study demonstrated significant improvement in arch and back pain, and reduction in knee pain.

The goal of the current study is to improve and extend our 2009 study, but introducing much more sophisticated measures for the parameters of interest. In 2009, we had concerns about the accuracy of some of the measures on radiographs. In the current study, both weightbearing radiographs and weightbearing CT scans will be utilized to gain a more accurate appreciation for the changes in morphology in three dimensions, that are anticipated. Subjective measures of pain were based on unvalidated scales and are replaced by only validated assessment tools. The previous study did not allow for standardization of shoes while the current study provides study shoes as well as insoles to all subjects.

The value of this study to patients who suffer from the most common foot ailments is evident. Arch supports are a simple treatment option for a variety of conditions including hallux valgus, metatarsalgia, pes plantar fasciitis, and may also be helpful for chronic ankle, knee, and back pain. Arch supports are a highly cost effective and potentially helpful way to manage a variety of simple conditions that may be otherwise treated surgically. The investigators hope that this study will demonstrate a safe, effective, and inexpensive way to help manage some of the most common foot ailments.

2. Specific Aims and Objectives

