The objective of this study is to measure the structural changes that occur in the foot when wearing arch supports, and how these changes correlate with overall relief of common structural-related foot ailments; plantar fasciitis, metatarsalgia, and/or hallux valgus

Specific Aim #1:

Measure any changes that occur in the position and alignment of the foot bones relative to one another using weight bearing radiographs and weight bearing CT scans, with and without over-the-counter arch supports under the sole of the feet.

Hypothesis: Arch supports (orthoses) will alter the positioning and alignment of the bones of the foot when standing. Any changes will be measurable in three dimensions, using both weight bearing CT scans and standard anterior-posterior and lateral radiographs.

Specific Aim #2:

Demonstrate if there is a correlation between symptomatic relief of painful foot conditions including hallux valgus, pes planus, metatarsalgia, as well as low back, knee and ankle pain using validated clinical scores and quality of life measures.

Hypothesis: Painful foot conditions as well as certain types of low back, knee, and ankle pain will improve when subjects wear over-the-counter arch supports on a regular basis, as demonstrated by validated subjective scoring.

3. General Description of Study Design

This study is a single armed prospective case series designed to evaluate the efficacy of treating common structural-related foot ailments (i.e. plantar fasciitis, metatarsalgia, and/or hallux valgus) with a high quality non-custom made arch support. It is believed that these conditions are the result of inadequate or poorly fitted arch supports resulting in a lack of structural correction in the foot while weight bearing. Over-the-counter insoles are believed to counteract the shortcomings in foot structure that result in these painful conditions. In this study, it is proposed that changes in foot morphology can be measured quantitatively using weight bearing CT Scan (Computerized Tomography) and X-rays of the subject with and without the arch supports. Subjects will also answer questions from a validated series of questionnaires pertaining to their foot condition and generalized health and activity level.

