- Pre-treatment assessment to be completed on day one.
- Subjects will describe their immediate impressions without and with the arch support in place.

Insole Selection

- Based on clinical assessment, properly sized set of arch supports and properly fitted athletic shoes will be dispensed to the study subject. Fit and comfort will be confirmed before proceeding with other data collection steps.

Baseline Measurements

- Each subject will have one weight bearing CT and one weight bearing X-ray series (AP/Lateral) taken barefooted and a second series taken with the selected arch support in place. Subjects are enrolled sequentially, and there is no placebo group.
- Image analysis will compare position and alignment of bones of the foot to measure differences in positioning with and without arch supports, using CT and X-ray. X-ray measurements will include intermetatarsal angles, hallux abductus angle, sesamoid position, metatarsal declination angle, calcaneal inclination angle, talocalcaneal angle, calcaneocuboid angle, and overall morphology. CT measurements will be used to determine the 3-dimensional positioning of the foot bones, and will document the change in position that occurs with and without arch support.

Logging of Activities and Symptoms

- Study subjects will be issued a diary and they are to record the following data on a weekly basis. The diary will be sent to the patient via email and RedCap links.
 - Estimated distance walked (Those able to count steps are encouraged to do so.).
 - Activities of Daily Living
 - Symptoms, and level of pain rated on a VAS scale.
 - Compliance with wearing of insoles and athletic shoes

b. Treatment Phase

We will be conducting follow up surveys via email and RedCap links with patients.

Monthly follow up (End of weeks 4, 8, and 12)

- Confirmation of eligibility based on inclusion/ exclusion criteria
- Medical history: New or relevant changes to medical history, including history of current disease, and information regarding underlying diseases will be recorded
- Review of logged data from daily diary
- Completion of physician re-assessment and OAS and VAS scoring.
- Validated questionnaires will be completed at each of the 3 follow-up visits.
 - ACFAS Universal foot Evaluation
 - AOFAS Outcome score
 - Oswestry Low Back Disability score
 - Pain Intensity Score
 - Global Health Test
 - Pain Interference
- Record any Adverse Events

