- Clinical photographs will be taken with and without the arch support in place, while barefooted.

c. Study Completion/Termination

When the subject completes the study, voluntarily withdraws, is withdrawn for any reason, the study is terminated, or the Investigator is no longer able to locate the subject, the reason for the withdrawal will be reported along with any relevant information concerning the device, subject condition or death.

All subjects withdrawn from the study due to an adverse event, or have an adverse device effect or serious adverse event at study completion, will be followed until the adverse device effect or serious adverse event is resolved, a resolution is no longer expected or it returns to baseline.

Treatment Discontinuation

After completing the estimated 12-week visit requirements, the subject will be considered to have completed the study. In all cases of withdrawal, the date and the reason for withdrawal are to be documented.

Primary Endpoint

The primary endpoint is the change in symptoms when arch supports are worn, as compared to baseline. Change in symptoms and relief of pain will be quantified based on subjective completion of validated questionnaires. Data from the questionnaires will provide a reliable assessment of symptomatic relief from the foot ailments being evaluated.

Secondary Endpoint

The secondary endpoint is the change in foot morphology when shoe inserts are worn. The change to be documented is the acute change that occurs in the boney structure of the foot when it is supported with the orthosis. A critical part of the analysis is to demonstrate if there are measurable changes in foot morphology when supported, and to determine if those changes correlate with symptomatic changes in the study subject's foot condition.

Remuneration

Study subjects will not be paid to participate in this study. However, all participants will receive new orthoses and new shoes, and will be permitted to keep these items at the conclusion of the study. Also, all study participants will receive up to \$50 to reimburse them for any travel expenses related to the study. We would like to pay the participants by check on the date of their visit, if permitted to do so.

Sharing of Data and Confidentiality

All data will be kept within the confines of MGH. Since there are no other sites involved in the study, no outside investigators will have a need for access to the data.

7. Risks and Discomforts

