The risks include discomfort during walking and/or standing, and can include bruise and/or blister formation, exacerbation of existing foot pain, tightness in shoes, temporary foot or leg cramps, bruising of the foot. X-rays and CT scans will be taken, and these tests involve very low levels of radiation. All of the devices being used in this study are currently available for purchase without a prescription, and are being used in the manner in which they were intended.

There are no new applications being explored for either the insoles or shoes that the study subjects will receive during this study. There are no unusual or excessive risks to study subjects, and all procedures being performed on subjects are already in use for diagnostic and treatment purposes.

8. Benefits

Historically, when these conditions (plantar fasciitis, hallux valgus, metatarsalgia) are treated with arch supports, they have responded with significantly less pain, and in many cases, helped the subjects to avoid surgical correction. We expect that the subjects who participate in this study will show signs of improvement in symptoms. They will also benefit from a highly focused medical examination of their

feet. Future patients will benefit from this study by knowing that arch supports are a safe and effective treatment for these foot ailments. The study may also help to optimize arch support design in the future.

9. Statistical Analysis

Statistical plan is for a one-way repeated measures ANOVA to compare the parameters with participants with and without arch-support insoles for each slope. We anticipate using SPSS for Windows (SPSS Science Inc., Chicago, IL, USA) for the statistical analyses. Levene's test will be used to test the homogeneity of the variances. A Kolmogorov-Smirnov test will be used to evaluate the normality of the data, a Wilcoxon test will be used when the data are not normally distributed. The significance level was set at $\alpha = 0.05$. The effect size (ES) for the difference from baseline will be calculated for each variable as a measure of the practical relevance of the significance using Cohen's d ; ES values between 0.20 and 0.49 are considered small, those between 0.50 and 0.79 are considered moderate, and those 0.80 and above are considered large.

10. Monitoring and Quality Assurance

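### Symptom change is credited to the arch supports alone, but every subject starts new fitted shoes and supports together, with no comparator

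*Combined protocol and SAP*

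**What the plan says.** The title is "A test of efficacy and foot position alteration in patients wearing Good Feet arch supports for the treatment of pain". Section 3 states: "This study is a single armed prospective case series", and goes on: "designed to evaluate the efficacy of treating common structural-related foot ailments". The treatment it names is a non-custom arch support. Sections 3 and 6a both say that there is no placebo.

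Section 1 gives the reason for the shoes: "The previous study did not allow for standardization of shoes while the current study provides study shoes as well as insoles to all subjects". Under Insole Selection in Section 6a, a "properly sized set of arch supports and properly fitted athletic shoes will be dispensed to the study subject", so both items arrive in one step. The Remuneration paragraph confirms that the shoes are new. The weekly diary has one bullet for wear: "Compliance with wearing of insoles and athletic shoes".

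The primary endpoint reads: "The primary endpoint is the change in symptoms when arch supports are worn, as compared to baseline". It does not mention the shoes. The Aim 2 hypothesis likewise expects improvement from wearing the supports. Section 8 adds: "Future patients will benefit from this study by knowing that arch supports are a safe and effective treatment for these foot ailments".

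Section 9 plans a one-way repeated-measures ANOVA comparing participants with and without the insoles at alpha 0.05. It also reports Cohen's d for the difference from baseline.

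**The concern.** Common shoes make footwear uniform between subjects during follow-up. Within each subject they also add a footwear change between the baseline score and every later score. Shoes and supports start together, so the symptom data cannot separate them. With no concurrent control, natural course and expectation are mixed in as well.

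At stake is the study's main conclusion. Followed as written, a significant change from baseline would be reported as efficacy of the supports, which this design cannot show. Someone reading only the title and the primary endpoint would not learn that the exposure is a package.

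**Working it through.** **Which measures have a with/without-support contrast?**

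| Measure | When | Contrast | What differs |
|---|---|---|---|
| X-ray and CT | Visit 1 | Barefoot vs support in place | The support, same day |
| Immediate impressions | Visit 1 | Without vs with support | The support, same day |
| Clinical photographs | Listed under monthly follow-up | Without vs with support, barefoot | The support, same occasion |
| Symptom questionnaires | Baseline, weeks 4, 8, 12 | Before vs after | Supports, new shoes, elapsed time, knowledge of treatment |

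The Section 9 contrast thus exists for the first three rows but not for the questionnaires, which carry the primary endpoint. No shoes-only run-in, washout or untreated period is described.

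**How small a change would be significant?** There is no planning figure to reproduce: the 50 subjects are stated without power, effect size, SD or dropout. What follows is illustration. From the plan: n = 50 (Section 4), alpha 0.05 and the small band 0.20 to 0.49 (Section 9). Assumed: two-sided test, between-visit correlation r, compound symmetry, and 40 completers (20% dropout) as a variant.

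*Two occasions.* The repeated-measures ANOVA equals a paired t-test (F = t²). The smallest significant observed change, in SDs of the change score, is t(0.975, n−1)/√n.
- n = 50: 2.0096/7.0711 = 0.284
- n = 40: 2.0227/6.3246 = 0.320
- On the baseline-SD scale, multiply by √(2(1−r)). For n = 50 and r = 0.3, 0.5, 0.7 this gives 0.336, 0.284, 0.220.

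*Four occasions, n = 50.* Under compound symmetry the error variance is half the variance of a change score, so F = (n × SS/3)/(1/2). SS is the sum of squared deviations of the four visit means, in SD-of-change units, and d is the change at week 12. The critical value on 3 and 147 df is 2.67.
- Plateau (0, d, d, d): SS = 0.75d², F = 25d², d = √(2.67/25) = 0.33
- Linear (0, d/3, 2d/3, d): SS = 0.556d², F = 18.52d², d = √(2.67/18.52) = 0.38

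Every threshold above lies in the small band.

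**Chance of significance if the supports do nothing**, for an assumed total non-support change (n = 50, noncentral t or F):

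| Assumed change (SD of change) | 0.2 | 0.3 | 0.4 | 0.5 |
|---|---|---|---|---|
| Two occasions | 28% | 55% | 79% | 93% |
| Four, plateau | 27% | 56% | 83% | 96% |
| Four, linear | 21% | 43% | 69% | 89% |

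**Order of baseline scoring (secondary).** The telephone script in Section 5 sends subjects to the store for fitting before the clinic visit. It then has them receive the items before it lists the tests and questionnaire. Section 6a labels the questionnaires pre-treatment and lists them before dispensing. But it puts an impression with the support in place in that same block, and under Insole Selection it has fit and comfort confirmed ahead of the other data collection. These passages can be followed in different orders.

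**The case against.** The strongest reply is that nothing is hidden. The protocol declares a single-arm case series without placebo and explains the shoes, and the endpoint is already worded as change from baseline. That is fair as to the missing comparator, and the single arm itself is not faulted here. It does not answer the shoe point: disclosing a single arm does not disclose, in the endpoint, a second intervention that starts with the first.

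Several further points stand:
- Only n and alpha come from the plan. The 0.28 threshold depends on choosing two occasions and a two-sided test; with the four scheduled occasions it is higher.
- Any within-subject test on 50 subjects flags small changes. That is not evidence of confounding.
- Section 9 asks for effect sizes to judge practical relevance, so the plan does not rest on significance alone. But Cohen's d would measure the same mixed change; it guards against over-reading a trivial change, not against misattributing it.
- The secondary endpoint asks only whether bone shift and symptom change correlate. It does not claim that a correlation proves an effect.
- The Section 8 sentence states an expected benefit and is not a planned inference.
- The diary form is not in the documents, so whether wear of shoes and insoles is captured separately is unknown.

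A reader might also infer that some baseline scores are taken after the items are worn. No passage says so, and Section 6a calls the scoring pre-treatment. Whether the store fitting involves trying the items on is not stated.

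**Conclusion.** The point holds as one of attribution. The symptom analysis can show change after study shoes plus supports, mixed with natural course and expectation. It cannot show efficacy of the supports, to which the title, Section 3, the Aim 2 hypothesis, the primary endpoint and Section 8 credit the change or the efficacy.

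At n = 50 an observed change of about 0.28 SD of the change score (two occasions) or 0.33 to 0.38 SD (four occasions) would be significant whatever its cause. This rests on two-sided testing and, for the latter range, compound symmetry and the assumed time course.

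Two stronger readings are not supported. One is that the shoes, or other non-support causes, will in fact produce a significant result: the documents give no size for such an effect, and the 30 days of pain at entry is only a minimum. The other is that the imaging results are compromised: that contrast is made on the same day and is specific to the support. Only its correlation with symptom change inherits the problem.

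The order of baseline scoring is a lesser ambiguity, not a demonstrated error.

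**What to change.** 1. Restate the primary endpoint in Section 6 as within-subject change in symptoms from baseline in subjects given study shoes plus arch supports. Align the Aim 2 hypothesis in Section 2.
2. Restate the efficacy wording in the title, Section 3 and Section 8 as uncontrolled pre-post change.
3. In Section 9, limit the with/without-insole comparison to the same-day contrasts (Visit 1 imaging and impressions, and the photographs). Describe the symptom analysis as change from baseline over weeks 4, 8 and 12.
4. Secondary: reconcile the store fitting and script order in Section 5 with the pre-treatment scoring, the with-support impression and the fit check in Section 6a. All baseline questionnaires should be completed before the items are dispensed for use and before the with-support impression. State whether the store fitting involves trying the items on; if it does, a Visit 1 order rule alone cannot guarantee scoring before any wear.

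The cost is wording and one order rule. No visit, procedure or subject is added, and the shoes stay, so the standardisation is kept. The downside is a narrower claim.

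### The primary endpoint names no questionnaire, visit, success rule or multiplicity rule, and Section 9 does not clearly assign it a test, so any one of six scales at an unadjusted 0.05 could be reported as the primary result

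*Combined protocol and SAP*

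**What the plan says.** **Endpoint (Section 6, Primary Endpoint).** "The primary endpoint is the change in symptoms when arch supports are worn, as compared to baseline". The only statement of how it is measured is that "Change in symptoms and relief of pain will be quantified based on subjective completion of validated questionnaires". No scale, visit, threshold or summary measure follows.

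**Instruments (Section 6a and 6b).** Six questionnaires are listed: ACFAS, AOFAS, Oswestry, Pain Intensity, Global Health and Pain Interference. They are given at baseline, and "Validated questionnaires will be completed at each of the 3 follow-up visits" (weeks 4, 8 and 12). VAS and OFS (OAS in Section 6b) scoring is also mentioned. It is unclear whether these are extra scales or shorthand for the listed forms.

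**Analysis (Section 9).** "Statistical plan is for a one-way repeated measures ANOVA to compare the parameters with participants with and without arch-support insoles for each slope". The plan then says "The significance level was set at" 0.05, with no testing order, adjustment or success rule. A Wilcoxon test replaces the main test if the data are not normal. "The effect size (ES) for the difference from baseline will be calculated for each variable", with labels for small, moderate and large but no value that must be reached.

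**The concern.** The endpoint names a class of instruments, not an outcome. Section 9 does not close the gap. Its contrast of insoles on versus off describes the day-1 imaging, where there is a barefoot series and "a second series taken with the selected arch support in place". It also fits the clinical photographs and the day-1 item "Subjects will describe their immediate impressions without and with the arch support in place". The questionnaire endpoint is a different contrast, follow-up against baseline. The reference to slopes matches nothing else in the protocol.

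Section 3 says the study evaluates efficacy, and the Aim 2 hypothesis predicts improvement shown by validated scores. If one scale of six reached p < 0.05, it could be offered as that proof. A reader could not tell a planned result from a selected one, and a p-value on a scale selected that way is not a test at the 5% level.

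**Working it through.** The plan gives no familywise error rate and no derivation of its 50 subjects, so there is no figure of its own to reproduce.

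**Inputs from the protocol.** n = 50 (Section 4); six questionnaires, baseline plus three follow-up visits (Section 6); alpha = 0.05 (Section 9).

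**Assumptions, not in the protocol.** No scale truly changes; any significant scale may be called primary; tests are two-sided; scales share a common correlation r.

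**1. Independent scales, one test each.**
- Either direction: 1 − (1 − 0.05)^6 = 1 − 0.7351 = 26.5%.
- Improvement only: 1 − (1 − 0.025)^6 = 14.1%, against 2.5% for one scale.
- Other counts: four scales (without Oswestry and Global Health) 1 − 0.95^4 = 18.5%; five (without Oswestry) 1 − 0.95^5 = 22.6%; eight (VAS and OFS counted separately) 1 − 0.95^8 = 33.7%.

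**2. Correlated scales, one repeated-measures ANOVA per scale.** Simulation with 50 subjects, four visits, all visit correlations equal at 0.6 (so sphericity holds) and 20,000 replicates. Improvement means p < 0.05 with the week-12 mean on the improved side of baseline.

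| r | Any of six, either direction | Improvement only |
|---|---|---|
| 0 | 26.7% (exact 26.5%) | 14.4% (exact 14.1%) |
| 0.5 | 21.4% | 11.1% |
| 0.7 | 17.0% | 9.3% |
| 0.9 | 11.4% | 6.2% |

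The number of visits does not alter these omnibus rates while sphericity holds.

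**3. Without sphericity.** Let follow-up visits correlate 0.4 with baseline and 0.8 with each other, and leave the ANOVA uncorrected. One scale then rejects about 7% of the time, and at least one of six about 23% (r = 0.7) to 36% (r = 0).

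**4. Each visit tested against baseline instead (six scales, three visits, paired t-tests).** With equal visit correlations: 37% (r = 0.7) to 55% (r = 0) in either direction. With the structure in step 3: about 29% to 46%. The range across both is about 29% to 55%. Changing the value of an equal visit correlation tests nothing here: changes from a shared baseline then always correlate 0.5. Only a different correlation pattern is a real sensitivity check.

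**5. What the remedy leaves detectable.** Two-sided paired t-test, 80% power from the noncentral t distribution, in units of the SD of the change score.

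| Alpha | n = 50 | n = 40 |
|---|---|---|
| 0.05 (one primary) | 0.40 | 0.45 |
| 0.05/5 = 0.01 (strictest Holm step, five secondary scales) | 0.50 | 0.56 |
| 0.05/7 (strictest Holm step, seven X-ray measures) | 0.52 | 0.59 |

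The 40 illustrates incomplete week-12 data; the protocol states no dropout rate.

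**The case against.** **Section 9 may be meant to cover the questionnaires.** The effect size is a difference from baseline for every variable, and a repeated-measures ANOVA over four visits would be a natural analysis. This stands in part. A reader might infer that the primary endpoint has no test at all, and the text does not support that; the test is merely not clearly assigned. One ANOVA per scale would also limit choice among visits, but not choice among scales, and the 11% to 26.5% figures already assume it.

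**The plan does not say that any significant scale counts.** True. It neither states nor excludes such a rule, so the rates show what the text permits and do not predict conduct.

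**Six is not a firm count.** Also true. The endpoint refers to foot ailments, which could remove Oswestry and perhaps Global Health; counting VAS and OFS separately would add two. The independent-scale rate runs from 18.5% to 33.7% across those readings, all well above 5%.

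**Review of data at each visit.** A reader might infer from Section 10 that outcomes are analysed as the study proceeds. The documents do not support that: the review is described as a subject-safety measure. It shows only that scores are visible in an open single-arm study.

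**This is a small case series in which attribution is the larger problem.** The study still declares a primary endpoint, an efficacy purpose and a significance level. Attribution is a separate weakness and no reason to leave the endpoint undefined.

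**Conclusion.** The concern holds and should be fixed before outcomes are examined. No primary scale, visit, success rule or multiplicity rule is given, and the test that Section 9 describes does not match a change-from-baseline endpoint. That conclusion rests on the text alone.

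The size depends on assumptions. With one ANOVA per scale under sphericity, the false-positive chance is roughly two to five times the nominal 5%, for assumed inter-scale correlations from 0.9 down to 0. Departures from sphericity raise it, and visit-by-visit testing raises it further by an amount that depends on unknown visit correlations. No single figure should be quoted as the study's error rate.

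**What to change.** Issue a dated amendment before any outcome data are summarised or compared across scales. It should state how much follow-up data had been collected and seen by then, because a choice made after scores are known would not cure the problem.

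- **Primary.** Name one foot or pain questionnaire already collected, at one visit; for example, change from baseline to week 12 in one named score. If a general pain score is chosen, state that it refers to foot pain.
- **Test.** Fix it in advance; for example, a two-sided paired t-test at 0.05, with Wilcoxon signed-rank as a sensitivity analysis and not as a switch triggered by a normality test.
- **Secondary.** The other five questionnaires at week 12, with Holm adjustment; weeks 4 and 8 supportive. Say whether VAS and OFS/OAS are separate scales and, if so, place them in this order.
- **Imaging.** Label the X-ray and CT measures and the symptom–morphology correlations exploratory, or Holm-adjust them.
- **Section 9.** Map the baseline-versus-follow-up test to the questionnaires and the insoles-on-versus-off test to the imaging. Define the slope condition or delete it.

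The cost is wording, with no added subjects, visits or data. The primary test keeps the full alpha (0.40 SD detectable with 50 subjects, 0.45 with 40). The power cost falls on the secondary scales (0.50 and 0.56 SD at the strictest step) and, if the seven X-ray measures are adjusted rather than called exploratory, on those too (about 0.52 and 0.59 SD). The change does not make improvement attributable to the arch supports.
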